Title: The Outcome of Sports Vision Training on Collegiate
Softball Players

NCT number: Not assigned.

Protocol ID: 2022-1225-EXP

Date: 04 Aug 2023

Protocol for Softball Study:

Goals to address in vision training: increase eye hand coordination, peripheral awareness, visualization, concentration, depth perception, anticipation, contrast sensitivity, target accuracy, and decrease reaction time.

There are 23 ladies on the softball team. There is an eight week vision training protocol developed, not including the pre-evaluation and post evaluations, wash out and final evaluation. The training will be a required once per week 45 minute training session. They will have signups for 2 per hour so we can ensure high quality training, with strict adherence to the protocol.

There are eight tasks for each session. It was recommended to change the order of the task each week to account for order effects. So I have different training sheets for each week stapled to their others for continuity. The week one training sheets are in the Softball Folder. Please be diligent in keeping track of time, as to not go over time. You must follow the specific order of activities each week. If a conflict arises, then please make a note on which activities were completed out of order.

I have timed the protocol to be 38 minutes when I walked through it so that leaves a few minutes for changing areas etc.

No one is allowed to engage with the study participants unless they have given me their CITI training, this includes the Optometry students. If in doubt do not engage with the participants.

Most of the activity's difficulty can be adjusted to be MORE difficult for progression. They cannot be made easier than the base protocol though, so please do NOT make any activity easier. If you run out of time to complete a task just note it.

General Coaching Guidelines:

1. Always use positive reinforcement. Patients should always be verbally rewarded for good effort. If a patient is unsuccessful at the required task, the therapist should encourage the patient and commend his hard work.
2. Always ask patient how their eyes feel and how they are doing throughout each task. The therapist should try to establish an awareness on the part of the patient of what they are doing to keep the targets clear, single, and visible as they accomplish the task. The therapist should encourage the patient to keep the eyes working together and keep the targets clear throughout each activity.
3. Active, enthusiastic coaching is critical to help the patients maintain motivation and engagement with the activities. If a patient is becoming frustrated, encourage them through the activity, and modify it to ensure it is difficult enough to challenge the patient, but not so difficult as to prohibit them from accomplishing any of the task.
4. Always respect the patient's training time. Avoid overtime in offering the vision therapy.

TASK DESCRIPTIONS AND PROGRESSION

-Brock string 3 minutes timed

- Fixation 1) The patient is comfortably standing. The feet are shoulder width apart, pointing straight ahead. 2) Instruct the patient to hold the string taut at her nose and ask him/her to look at the closer bead (let's say green bead and red beads are placed closer and farther respectively) and describe what he or she sees. Because of physiological diplopia, the patient should report that he/she sees one green bead and two red beads. In addition, the patient should perceive two strings crossing the green bead (or "X" at the green bead), with one string extending from his or her right eye and the other appearing to extend from his or her left eye. 3) Ask the patient to fixate the far bead, and he/she should now report one red bead with the strings crossing at the red bead. The patient will also see two green beads.
- Smooth Vergence 1) Using the same set up instruct the patient to fixate on the closest bead. While he/she is fixating on the closest bead, move it slowly towards the farther bead. The patient should be appreciating accurate fixation without suppression at all times. Once it reaches the farther bead, slowly bring it back to its original position while he/she is fixating on the moving bead. 2) Repeat the procedure until the patient can comfortably perform the task. Change the distance and speed to make the task more challenging.
- Jump Duction 1) Set 3 beads at 1, 2, and 3 feet. Instruct the patient to fixate on the closest bead for a few seconds, and then to fixate on the second and third beads for a few seconds each. Then instruct the patient to fixate on the middle and the closest beads. Repeat the procedure until the patient can comfortably perform the task. 2) Move the closest bead closer to the patient and repeat the procedure.
- Bug on a String 1) Use the two beads set at 1 and 2 feet from the patient. He/she initially fixates on the closest target appreciating the "X" at the bead. Ask the patient to slowly move the "X" from the closest bead to the second bead until the "X" is at the second bead. Once he/she reaches the second bead, instruct him or her to slowly move it back to the first bead. Repeat this a few times. 2) Once it becomes easier, instruct the patient to move the "X" much slower. 3) Also increase the distance between two beads to make the task more difficult.

Fixation only needs to be explained the first week, then you can confirm, are you seeing it correctly? Then move on to smooth vergence, again this could just be done during the first week and then more advanced exercises can be performed at other sessions. After the athlete is comfortable with fixation and smooth vergence, move on to jumps and bug on a string. We can incorporate multiple strings to progress difficulty, or you can also use BOP/BIM (Base-out Plus/ Base-in Minus). Introduce Plus lenses OU when the patient is converging (i.e., fixating at the closest target). Introduce Minus lenses OU when the patient is diverging (i.e., fixating at the farthest bead). Just note any progression details for continuity. Please start with 3-beaded strings and only advance to the 5-beaded strings when looking to increase difficulty.

-Strobe goggles 6 minutes timed

Ask the required screener question, "Do you have history of epilepsy or seizures?" before use. We will be using strobe goggles in setting A (binocular strobing, OD/OS at the same time). This is a timed activity, 6 minutes. Start at level 1 the first week. The strobe goggle level can increase as the participant becomes proficient, which is noted by 6 glove hand catches in a row.

Record the level of strobe and what task ended on. Tasks are included below:

1. Catching
 - a. Pair the subject with another person.
 - b. Instruct the subject to catch tennis balls as they are tossed in their direction
 - i. Option Level 1: bounce pass to athlete, using either both hands or glove hand but athlete cannot advance to next strobe goggle level until successfully catching 6 with glove hand only
 - ii. Option Level 2: balls tossed from the air at chest height, using either both hands or glove hand but athlete cannot advance to next strobe goggle level until successfully catching 6 with glove hand only
 - iii. Option Level 3: two different color balls used, subject catches the ball based on the pre-announced catching style for each color. Balls tossed from the air or bounced from the ground, athlete must try to catch the red ball in a high-hand way and the green ball in a low-hand way (colors may vary, just choose two different color balls that athlete must distinguish for either a high- or low- catch). Cannot advance to next strobe goggle level until successfully catching 6 with glove hand only
 - iv. Option Level 4: duplicate levels 1-3, with two balls and catching with both hands simultaneously. Cannot advance to next strobe goggle level until successfully catching 6 consecutive balls

-Eye Metrix Double Eye speed scanning timed 3 minutes

I will be re-arranging the eye metrix board weekly.

Be mindful of head movement, use just your eyes. Give them a laser pointer to follow along and ensure accuracy. They should use scanning techniques and grouping. Use the two number boards, this will be timed so they will start for example at 50 and work their way down, finding as many numbers as possible while alternating boards for the even and odd numbers, or every other number switch to the other board. Record what number they make it down to. If they are able to find all 50 numbers before 3:00 is done, then instruct them to start over at 50 and work their way back down and then record the total number of numbers found (50-1, 50-42)

-Synchrony

Using the synchrony light rail and the cell phone. There will be four tasks, they will do each task twice. They are titled "SB Research Inbound", "SB Research Outbound", "SB Research SLOW Inbound", "SB Research Go/ No go". The participants will "step in" and "step out" of the "batting box" for each task trial, this is to simulate their batting procedures. Have the participant stand in their batting stance in

orientation to the light rail. Use the hand held trigger. Record the Average Error and the Smallest Error of the best of the two trials.

Inbound: This is a timing task, the red/green flashing light will travel towards you at a high rate of speed (10-20mph variable) while green. You will anticipate when the green light is going to reach the white light target that is close to you, and respond with the trigger when the light is aligned with the target.

Outbound: This is another timing task, the red/green flashing light will travel away from you at a high rate of speed (10-20mph variable) while green. You will anticipate when the green light is going to reach the white light target that is at the far end of the light rail, and respond with the trigger when the light is aligned with the target.

SLOW Inbound: This is a timing task, the red/green flashing light will travel towards you at a slow rate of speed (8-12mph variable) while green. This is to mimic a slow pitch. You will anticipate when the green light is going to reach the white light target that is close to you, and respond with the trigger when the light is aligned with the target.

Go/ No go: You will see a white light as your target close to you. At the far end of the light rail you will see a flashing green/red light that will move towards you at a high rate of speed (10-20mph variable), it may turn red or it may turn green. If it stays green you will react, as green is "go" and try to hit your mark, aligning the green light with the white target. If the moving light turns red, you will not react, as red is "no go".

-Near Far Shift on Senaptec

Use setting "SB Research". Perform this three times and record their best score; the higher score is the better score. Have the participant stand at the 10 foot sticker, hand them the cell phone. Explain they want to go as fast as possible. Starting on the large screen three letters will appear, then on the phone at near, alternating back and forth. Two of the letters will point in the same direction, you must swipe on the cell phone in the direction that the two letters are with the similar orientation. Then switch your focus to near, to the phone and complete the same task. Cycle back to the large screen etc. Hold the phone up high to make the switch easier. You are penalized for wrong answers so maintain accuracy.

-Spatial Memory on Senaptec

Use setting "Softball 8". Perform this three times and record their best score; the best score is closest to zero since it's calculating distance error. Have the participant stand 2 feet from the large screen. Explain this is not for speed. There will be 8 baseballs that will be the targets, they will appear all at once, across the screen in various locations. The participant will have to remember where they were displayed and once they disappear tap the screen in the location the 8 targets were.

-Dynavision

Use "Proactive 60 seconds, 4 digit" and "Reactive 60 seconds, 4 digit settings". Perform each setting twice and record the best score and average reaction time. Adjust the height of the board for the athlete to touch the top and bottom buttons comfortably. Explain they are hitting as many of the red

lights, as quickly as possible once they light up, use GLOVE HAND ONLY. Use your peripheral vision to detect the lights, there will be a central stimulus of 4 digits you must verbally call out as they appear.

Explain the two modes; Reactive the lights will disappear if you are not quick enough. Proactive the lights will stay lit until you tap and deactivate it.

-SVT Go No Go

Use the setting “Research Softball Go-No go”. Repeat it twice, record their best score. Adjust the height of the board if needed. The participants must touch/deactivate the lights as quickly and accurately as possible using BOTH HANDS. They must recognize and decide to react or not react based on the colors given to them for Go, and No Go. Go will be yellow, like a softball. Brown will be No Go. The stimulus interval can be decreased by 50um intervals if the participants are achieving over 75% accuracy of Go. The interval cannot be increased to make it easier. Record % Go, % No Go and Time Interval.

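### If main outcome 2 is scored at training sessions whose task order all athletes share, the weekly order change confounds task position with time; name the scored sessions and use one order at them.

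*Protocol*

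**What the plan says.** The opening section of the protocol sets eight tasks per weekly session over eight weeks and varies their order by week: "It was recommended to change the order of the task each week to account for order effects". The order is carried on printed sheets: "So I have different training sheets for each week stapled to their others for continuity". Staff are told "You must follow the specific order of activities each week", and departures are foreseen: "If a conflict arises, then please make a note on which activities were completed out of order". No order specific to an athlete and no randomisation of order is described. The sheets themselves are not in the documents.

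The same section places other assessments outside the eight weeks ("not including the pre-evaluation and post evaluations, wash out and final evaluation") and gives no task order for them.

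The SAP describes a within-subject before-after design and mentions no control group. Main outcome 2 sets baseline training performance against post-training performance on activities given only as examples (Dynavision and the Senaptec Sensory Trainer), using a Student's t-test. The SAP also plans a repeated measures ANOVA with corrected post-hoc t-tests, without saying which outcomes or time points enter it. It includes no position or order term, and it does not name the sessions that supply the scores.

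**The concern.** Rotating the order by week can balance position only over the whole run of weeks. A comparison of two sessions does not use that balance. If every athlete does a task sixth at the baseline session and second at the post-training session, the effect of moving four places enters every athlete's change score. It then looks the same as a training effect. Recruiting more athletes would not shrink it.

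The exposed analyses are a baseline-to-post t-test and a first-versus-last post-hoc contrast after the ANOVA. At stake is whether a gain or loss reported for a single activity reflects training or where the activity fell in the two sessions.

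The protocol itself treats order effects as worth guarding against. It also suggests one way they could arise: "If you run out of time to complete a task just note it" would fall mainly on tasks placed last. Near Far Shift and Spatial Memory are scored as the best of three trials and Dynavision as the best of two, so a trial lost to the clock lowers the expected best.

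**Working it through.** The documents give no position effect, SD, correlation, alpha or power, so there is no planned figure to reproduce. What follows is illustration.

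**Inputs from the documents.** 23 athletes (the team roster, assuming all take part and complete) and 8 tasks per session.

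**Assumptions.** Position effect δ linear, 0 to 0.05 SD per position; pre-post correlation r of 0.5 to 0.7; paired t-test, two-sided 0.05; no training effect; every athlete follows the same order at each scored session; the two orders are unrelated.

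**Step 1, shift in position.** For two unrelated orders of 8 tasks, P(shift = k) = (8 − |k|)/64 for k = −7 to 7. The mean signed shift is 0. The mean absolute shift is 2 × (7 + 12 + 15 + 16 + 15 + 12 + 7)/64 = 168/64 = 2.625 positions.

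**Step 2, bias and test.** Bias in the mean change = kδ. In SDs of the paired change this is d = kδ/√(2(1 − r)); the divisor is 1.000 at r = 0.5 and 0.775 at r = 0.7. The t statistic has 22 df and noncentrality d√23. The critical value is 2.074.

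**Step 3, chance that a task with no true change is declared improved, averaged over k** (first figure r = 0.5, second r = 0.7):

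| δ per position | uncorrected 0.05 (nominal 2.5%) | 0.05/8 (nominal 0.31%) |
|---|---|---|
| 0 | 2.5%, 2.5% | 0.31%, 0.31% |
| 0.01 SD | 2.6%, 2.7% | 0.34%, 0.36% |
| 0.02 SD | 3.0%, 3.4% | 0.43%, 0.51% |
| 0.05 SD | 5.8%, 8.0% | 1.25%, 2.13% |

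False worsening has the same rates. The SAP plans a multiplicity correction but names neither method nor family; Bonferroni over 8 is an example. A correction lowers the rates but leaves the bias kδ unchanged.

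**Step 4, one actual pair of orders.** The averages hide a wide spread. At δ = 0.05 SD and uncorrected 0.05, a favourable move of one position gives 4.2-4.8%, four positions 15-22%, and seven positions 36-54%.

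**Step 5, do shifts cancel across tasks?** Positions sum to 36 in any order of eight, so the eight shifts sum to zero. Brock string yields progression notes but no score. The seven remaining shifts therefore sum to minus the Brock string shift, which can lie anywhere from −7 to 7. Their mean can be as large as 7/7 = 1 position, and a smaller scored subset can be further from zero.

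**Step 6, the fix.** With one order at all scored sessions, k = 0 for every task. The bias is then zero and the rate is 2.5% in each direction, whatever δ is, provided the effect is additive.

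**The case against.** **The scores may not come from training sessions.** The SAP says the outcomes are evaluated after completion and compares baseline with final values. That wording fits the separate evaluations, and on that reading the weekly rotation does not bear directly on main outcome 2. This stands as an open alternative. Against it, the SAP speaks of training performance, and the protocol has these scores recorded within the training tasks. The scored sessions need naming on either reading.

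**The order may not be shared, or not fully.** Each athlete has a stapled packet, and nothing says whether packets differ. Two sign-ups per hour for 45-minute sessions suggest that athletes may overlap and sometimes swap tasks. This stands in part: departures noted as out of order would make the confounding partial, while the figures above assume it is complete.

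**The protocol never claims that rotation protects this contrast.** Correct. Rotation may serve training delivery, since no task need always come last. A reader might infer that the protocol offers a safeguard that fails; the documents do not say that it was meant for main outcome 2.

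**The ANOVA might use all weeks.** If so, position is spread over the weeks in the overall test, but a first-versus-last contrast stays exposed.

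**The size is assumed throughout.** Also correct. At 0.02 SD per position the inflation is slight. Under a simple cyclic rotation, seven of the eight tasks would move only one place between weeks 1 and 8, and one would move seven.

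**The lost-trial route is not what the model computes.** It acts at the end of a session, not linearly. With "I have timed the protocol to be 38 minutes when I walked through it" in a 45-minute slot there are 7 minutes of slack. It remains a possible route, with no frequency attached.

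**Conclusion.** The point holds in conditional form. If training sessions supply the scores for main outcome 2, and if athletes share each week's order, task position is confounded with time in the baseline-to-post comparison. Both conditions are natural readings; neither is stated. Under the assumptions above, false improvement for a single task averages 3.0-3.4% at 0.02 SD per position and 5.8-8.0% at 0.05 SD, against 2.5% nominal. The true effect may be zero, and a shift can hide a gain as easily as mimic one.

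Two stronger readings should be resisted. A reader might infer that main outcome 2 is biased as planned; the documents do not establish the scored sessions, the shared order or any position effect. A reader might also infer that shifts cancel, so that an overall gain across tasks is safe. That would need all eight tasks to be scored with a common slope, and the SAP lists activities only by example. Main outcome 1, the Senaptec re-evaluation, is not directly affected.

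This is a cheap improvement, not a demonstrated error.

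**What to change.** Add one sentence to the SAP stating which sessions supply the baseline, post-training and final scores for main outcome 2, and that one identical task order is used at all of them. Keep the weekly rotation for the other sessions. If the separate evaluations turn out to be the source, the same sentence settles their order, which is now unstated.

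The cost is that sentence and reprinted sheets for the scored sessions, with no added session time, staff or data.

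The change removes an additive position effect only. It does not separate training from practice or the passage of time. Nor does it deal with scores taken at changed difficulty, such as a shortened interval on the SVT Go No Go task, or with tasks noted as unfinished or out of order. The Eye Metrix layout also changes ("I will be re-arranging the eye metrix board weekly"), which matters only if that task is scored as an outcome.

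### The coaching rules make no exception for scored runs, so unscripted prompting can enter SAP outcome 2 if its values come from the training sessions

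*Protocol*

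**What the plan says.** **Coaching.** The General Coaching Guidelines stand before all eight task descriptions. Item 2 says "Always ask patient how their eyes feel and how they are doing throughout each task" and adds: "The therapist should encourage the patient to keep the eyes working together and keep the targets clear throughout each activity". Item 3 says "Active, enthusiastic coaching is critical to help the patients maintain motivation and engagement with the activities". No wording, amount or timing of prompts is given, and no trainer is assigned to an athlete.

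**Difficulty.** For a frustrated athlete, item 3 has the trainer adapt the task so that it stays demanding, within this limit: "but not so difficult as to prohibit them from accomplishing any of the task". The opening section of the protocol says: "They cannot be made easier than the base protocol though, so please do NOT make any activity easier".

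**Recording.** The only scoring instructions sit inside the training task descriptions. Scores are recorded for Eye Metrix, Synchrony, Near Far Shift, Spatial Memory, Dynavision and SVT Go No Go. For Dynavision, "there will be a central stimulus of 4 digits you must verbally call out as they appear". On the sheets, the opening section says: "So I have different training sheets for each week stapled to their others for continuity".

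**Analysis.** The SAP describes a within-subject before-after design. Main outcome 1 is a Senaptec Sensory re-evaluation against baseline. Main outcome 2 compares baseline with post-training performance on training activities, and gives Dynavision and the Senaptec Sensory Trainer as examples. The SAP does not say which visits supply the outcome 2 values.

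**The concern.** A score meant to measure visual skill should be obtained under the same conditions each time. Here the written rules ask the person running the task to question and encourage the athlete while it is in progress, and leave what is said, how often and by whom to the trainer. The protocol itself treats coaching as critical to motivation and engagement, so it cannot also be assumed to have no bearing on speeded or attention-demanding scores.

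In one group without a control, nothing absorbs a change in conduct between the two time points. If prompting differs between baseline and final runs, the difference is counted as training effect or subtracted from it. If prompting merely varies from trainer to trainer, it adds noise to the change. Neither can be removed in the analysis, because the plan does not ask for prompting to be recorded.

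**Working it through.** The plan states no sample-size calculation, alpha, effect size or SD, so there is no figure to reproduce. The check is mainly a comparison of texts.

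**Step 1. Do the coaching rules reach the scored runs?** Item 2 covers each task and each activity. The scoring instructions are for those same tasks, and nothing sets apart silent or standardised runs. On the text, the answer is yes for the training sessions.

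**Step 2. Where must prompting fall inside a run?**

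| Task | Run structure (protocol) | Recorded | Gap for a prompt between runs? |
|---|---|---|---|
| Eye Metrix | one timed run, 3 minutes | number reached | no |
| Synchrony | four tasks, each twice, stepping in and out | errors from the better of two trials | yes |
| Near Far Shift | three runs | best | yes |
| Spatial Memory | three runs | best | yes |
| Dynavision | two 60-second settings, each twice | best score and average reaction time | yes, but speech is already part of the run |
| SVT Go No Go | two runs | best; % Go, % No Go, interval | yes |

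Eye Metrix leaves no gap. Dynavision leaves gaps, but a question asked during a run competes with digits that the athlete must say aloud.

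**Step 3. Do these scores feed an outcome?** Outcome 2 is worded as training performance, and the training tasks hold the only recording instructions. That makes these sessions a natural source, but the SAP does not confirm it. The pre-, post- and final evaluations are described as lying outside the eight-week training protocol, and the guidelines are not stated to govern them.

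**Step 4. What could a shift in coaching do?** This is an illustration only, and the shifts are assumed. Take n = 23 (the team size in the protocol), a paired t-test with 22 degrees of freedom and no true change in skill. Let coaching differ between the two runs so that the mean change moves by d SDs of the differences. The chance of a significant result is

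1 − F(t*; 22, d√23) + F(−t*; 22, d√23),

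where F is the noncentral t distribution function and t* the two-sided critical value.

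| d (assumed) | d√23 | alpha 0.05 | alpha 0.05/8 = 0.00625 (assumed Bonferroni) |
|---|---|---|---|
| 0.1 | 0.48 | 7.4% | 1.2% |
| 0.2 | 0.96 | 15.1% | 3.2% |
| 0.3 | 1.44 | 28.0% | 7.9% |
| 0.5 | 2.40 | 63.0% | 29.6% |

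**Step 5. What if coaching only adds noise?** Let it add a fraction v to the variance of the change, with an assumed true change of 0.6 SD. The effective size is 0.6/√(1+v). Power at two-sided 0.05 is 78.5% for v = 0, 74.6% for v = 0.10, 69.2% for v = 0.25 and 61.3% for v = 0.50.

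**Step 6. Are the difficulty rules consistent?** For a task already made harder, they can be read together: the trainer may step back, with the base protocol as floor. For an athlete frustrated at base level, item 3 calls for modification while the opening section forbids easing. Those two passages contradict each other and must be reconciled.

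**The case against.** The strongest reply has four parts.

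- **Visits.** The guidelines belong to the training weeks, and the evaluations lie outside them. If outcome 2 is measured at evaluation visits, the rules may not apply. This stands, and it is why the point is conditional and why the visits must be named. A reader might infer that both main outcomes are contaminated. The documents do not show this for outcome 1.
- **Timing.** On multi-run tasks, questions can be asked between runs, and much of item 2 reads as if written for vergence work such as the Brock string. This stands for most tasks, but not for Eye Metrix, and the text does not confine prompts to the gaps.
- **Constancy.** Coaching that is the same at both time points largely cancels in a within-subject change. True, but the plan fixes neither trainer nor content, so constancy is left to chance. Equally, a reader might infer that the net bias inflates the change. Nothing in the documents fixes its direction.
- **Scoring.** Because the best run is kept, an interruption of one Dynavision run need not lower the recorded best score. This stands, so seconds lost to one exchange cannot be turned into a percentage gain.

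Two further inferences go too far. The sheets are stapled together, and that they carry the scores is a close inference from the recording instructions, but nothing says athletes see earlier results. Nor is it shown that baseline runs on the devices were eased: those tasks use fixed named settings, and the SVT interval may not be lengthened.

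**Conclusion.** The concern holds in a limited form. The written rules permit, and on their plain wording require, unscripted prompting during runs that are scored. If outcome 2 draws on those sessions, differences in prompting between trainers or over time can enter its change scores. The exposure is plainest for Eye Metrix and Dynavision.

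Size and direction cannot be computed from the documents. The illustrative figures rest on assumed shifts, 23 complete pairs and assumed significance levels. They show only that a modest systematic shift would matter in a sample this small. The contradiction over difficulty for an athlete frustrated at base level stands without any assumption about bias. The change should be made because it is cheap and the problem cannot be repaired afterwards, but no distortion of results has been demonstrated.

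**What to change.** 1. State in the SAP which sessions supply the baseline and post-training values for outcome 2.
2. State in the protocol that, in those sessions, each task has one fixed instruction script, no prompts or encouragement are given while a run is in progress, and comfort questions are asked only between runs. The athlete may still stop at any time.
3. Record those scores on a fresh sheet, with earlier sheets out of view.
4. Reconcile item 3 of the coaching guidelines with the opening section's rule on making activities easier.

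Coaching in all other sessions stays as written. The cost is about one paragraph and a separate score sheet, with no extra staff or visits. The drawback is that the scored sessions will be slightly less motivating for the athletes.

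### The seizure-history question is tied to the strobe goggles, so an athlete can meet Synchrony's flashing light before it is first asked

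*Protocol*

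**What the plan says.** **Strobe goggles (Protocol, Task Descriptions and Progression).** The trainer must ask "Do you have history of epilepsy or seizures" before the goggles are used. The exposure is a timed 6 minutes, described as follows: "We will be using strobe goggles in setting A (binocular strobing, OD/OS at the same time". The text does not say what happens after a positive answer.

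**Synchrony (same section).** There are four tasks, each done twice. The Inbound description reads "the red/green flashing light will travel towards you at a high rate of speed (10-20mph variable) while green". Outbound and SLOW Inbound describe the same kind of flashing light, and Go/No go includes "At the far end of the light rail you will see a flashing green/red light that will move towards you at a high rate of" (quotation cut short here). None of the four includes a screening question.

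**Session structure (Protocol, opening section).** "The training will be a required once per week 45 minute training session". Each session holds eight tasks. On order, the protocol says: "It was recommended to change the order of the task each week to account for order effects". The weekly orders are on training sheets that are not reproduced. Trainers are told to keep to the week's order, to make a note if tasks are done out of order, and to make a note if time runs out on a task.

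**SAP.** The design is a within-subject before-after comparison of baseline with final values. The SAP does not say how an athlete who completes only part of the programme is handled.

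**The concern.** The protocol itself makes seizure history a required question before one flashing-light device. A second device that it also describes as flashing has no such step, and nothing in the supplied text makes the goggle station come first. The precaution therefore depends on the order of stations, which the protocol deliberately varies.

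Two things are at stake. The first is participant safety: the question may come after an exposure to which the sponsor might consider it relevant. The second is who is in the before-after comparison. The question is first put during training, so a positive answer emerges after the pre-evaluation. The athlete's status would then have to be settled with baseline data already collected, in a programme whose weekly session is mandatory and contains eight tasks.

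**Working it through.** The plan states no figure on this point. The check is a comparison of the task descriptions, followed by a count of the trials that could precede the question.

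**1. Flashing stimulus and screening, by task**

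| Task, in listed order | Described as strobing or flashing | Screening question |
|---|---|---|
| 1 Brock string | no | no |
| 2 Strobe goggles | yes | yes |
| 3 Eye Metrix | no | no |
| 4 Synchrony (all four tasks) | yes | no |
| 5 Near Far Shift | no | no |
| 6 Spatial Memory | no | no |
| 7 Dynavision | no | no |
| 8 SVT Go No Go | no | no |

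Two of the eight tasks are described as strobing or flashing, and one of those two carries the question.

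**2. Synchrony trials per session**

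4 tasks × 2 trials = 8.

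**3. Trials before the question is first asked**

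Once an athlete has answered, her history is known, so only Synchrony trials before her first visit to the goggle station count. Let k be the session in which she first reaches that station. At most 8 × (k − 1) trials fall in earlier sessions, plus 8 more if Synchrony precedes the goggles in session k.

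- k = 1, listed order (goggles 2nd, Synchrony 4th): 0 trials.
- k = 1, Synchrony before goggles: 8 trials.
- k = 2: at most 8 × 1 + 8 = 16 trials. This requires the goggle station to have been missed in week one.

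**4. How likely is Synchrony first in week one?**

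The week-one sheet is not shown, so the documents allow anything from 0% to 100%. Two assumed schemes illustrate the range:

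- All orders of eight tasks equally likely: 20,160 of 40,320 orders put Synchrony before the goggles, which is 50%.
- The listed order rotated cyclically: 2 of 8 rotations do so (those starting at Eye Metrix or at Synchrony), which is 25%.

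Neither scheme is stated in the protocol, and the point does not depend on either.

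**5. Could the goggle station be missed?**

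The protocol allows for running out of time on a task. Its own walk-through took 38 of the 45 minutes, leaving 45 − 38 = 7 minutes for moving between areas and overruns. A missed station is therefore possible, but the timing does not make it the expected case.

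**The case against.** The strongest opposing case has four parts.

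**The screen may exist elsewhere.** The protocol text reads as a station manual for trainers. It has no eligibility or enrolment section, and consent pages were removed from the public copy. A reader might infer that this is the trial's only safety screen. The documents cannot establish that, and the point is limited to the supplied text.

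**The two devices are not shown to be equivalent.** The goggles strobe both eyes for 6 minutes. Synchrony is a light on a rail, with no flash rate, brightness or flash duration given, and it is unclear whether the light keeps flashing while it travels. Extending a goggle precaution to the rail is a clinical judgement. This stands: no harm from Synchrony is demonstrated, and whether the answer matters there is for the sponsor and investigator to decide.

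**The exposure is easily overstated.** A reader might multiply 8 trials by 8 weeks and speak of 64 unscreened trials, or say that half of all weeks are affected. Both treat every week as if the question had never been asked. An answer given in week one is known from then on, and each athlete's weekly sheets are kept together. Reaching 64 would require the question to go unasked through all eight Synchrony sessions, which the documents do not describe. This objection stands.

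**No consequence is stated.** A reader might infer that an athlete who answers positively is kept off the goggles but still put through Synchrony. The protocol says neither. The mandatory session and its eight tasks leave the matter unresolved, without settling it that way.

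What survives is narrower. The protocol requires the question, places it at one of two flashing-light stations, and does not ensure that this station comes first.

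**Conclusion.** The point holds as a safeguard placed inconsistently within the supplied text. The exposure before the question is 0 to 8 Synchrony trials per athlete if the goggle station is reached in week one, and more only if it is missed. At most 23 athletes are involved. The documents give no seizure history for the team, so the number who would answer positively is unknown, and any effect on the before-after comparison cannot be quantified.

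The conclusion rests on three conditions: that no screen sits on the removed consent pages, that the week-one sheet does not guarantee goggles before Synchrony, and that an answer once given is carried forward. If either of the first two fails, the ordering problem largely disappears. The protocol would still not say whether the answer bears on Synchrony, or what follows a positive one.

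The change is worth making because it costs almost nothing and bears on participant safety.

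**What to change.** Ask the existing question once, and record the answer for each athlete, before the pre-evaluation and before any flashing-light task. If this is already done at consent, the protocol should say so.

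The sponsor and investigator should also reconcile the Strobe goggles section with the Synchrony section and with the mandatory eight-task session in the opening section. The reconciled text should state whether the answer bears on Synchrony and what a positive answer means for participation. Those decisions are theirs, and no rule is proposed here.

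The cost is one form item and a line or two of protocol text. The only downside is that an athlete's status may be settled before baseline instead of later, which for a before-after analysis is the better time to settle it.
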